This is a randomized controlled trial, parallel-group, where 120 male blood donors were randomized 1:1:1 for donation over 16 weeks to:

- High-frequency plasma donors (HFPDs) donating plasma 3 times every 2 weeks (in total 24 times)
- Regular-frequency plasma donors (RFPDs) donating plasma once every 2 weeks (in total 8 times)
- The control group (controls) donating whole blood every 3 months (in total 2 times)

The study was conducted at the Blood Centre of Innlandet Hospital Trust from January 2022 to July 2024.

Trial Population

Established male blood- and plasma donors aged between 18 and 64 years were screened for eligibility. The inclusion criteria were sufficient levels of Hb, TSP, and IgG, an estimated blood volume (EBV) of at least 4500 mL, a donation history of at least one previous plasma donation, and the donors had to meet the eligibility criteria for both whole blood and plasma donation by plasmapheresis. Donors with a history of repeated measurements (>2) of haematocrit >50 % before enrolment were excluded.

All participants provided written informed consent. The study was approved by the Regional Committee for Medical and Health Research Ethics in Southeast Norway (2021/238929/REC Southeast A) and was conducted in accordance with the Declaration of Helsinki. The study is registered at clinicaltrials.gov (identifier: NCT05179200).

Intervention

The plasmapheresis procedure was performed using the Aurora Plasmapheresis machine, Fresenius Kabi. The plasma donation volume was 720 mL, including AC, which corresponds to approximately 650 mL plasma, excluding AC, assuming a haematocrit of 44% and an ACR of 100:6. The whole blood donations were 450 mL of whole blood.

Data Collection

Baseline data were collected through questionnaires and from the blood centre's database, LabCraft.

Blood Samples and Analyses

One tube of 6 mL EDTA plasma was collected non-fasting per participant immediately before the plasmapheresis procedure, at:

- Baseline week 1 (W1): Before the first donation in the study, after at least two months of no donation.
- End point week 18 (W18): Two weeks after the final donation.

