The plasma samples were centrifuged at 2200×g for 10 min immediately after collection, transferred into aliquots of 500 µL, and frozen at -40°C within 3 hours after collection. Within 3 months of storage, the samples were transferred to storage at -80°C until analysis. The samples were shipped on dry ice to the laboratory for analysis. PFAS analyses were conducted at the Environmental Pollutant Laboratory, University Hospital of North Norway, Tromsø, Norway, according to the method described by Huber and Brox [12]. Samples were analysed in two batches of 96 samples in 2023 and 122 samples in 2024.

Variables

Outcome Measures

Difference in plasma concentrations between W1 and W18 of the following PFAS:

Primary outcomes:

- Perfluorooctanoic acid (PFOA)
- Perfluorooctane sulfonic acid (PFOS)*
- Perfluorohexane sulfonic acid (PFHxS)*
- Perfluorononanoic acid (PFNA)
- Sum of PFOA, PFOS, PFHxS and PFNA [13]

Secondary outcomes:

- Perfluorobutanoic acid (PFBA)
- Perfluoropentanoic acid (PFPeA)
- Perfluorohexanoic acid (PFHxA)
- Perfluoroheptanoic acid (PFHpA)
- Perfluorodecanoic acid (PFDA)
- Perfluoroundecanoic acid (PFUDA)
- Perfluorododecanoic acid (PFDaDA)
- Perfluorotridecanoic Acid (PFTrDA)
- Perfluorotetradecanoic acid (PFTeDA)
- Perfluorobutane sulfonic acid (PFBS)
- Perfluoropentane sulfonic acid (PFPS)
- Perfluorooctane sulfonic acid (PFHpS)*
- Perfluorononane sulfonic acid (PFNS)*
- Perfluorodecane sulfonic acid (PFDS)*
- Perfluorodecane sulfonic acid (PFDaDS)
- Perfluorooctane sulfonamide (PFOSA)*
- 4:2 Fluorotelomer sulfonic acid (4:2 FTSA)
- 6:2 Fluorotelomer sulfonic acid (6:2 FTSA)
- 8:2 Fluorotelomer sulfonic acid (8:2 FTSA)
- 10:2 Fluorotelomer sulfonic acid (10:2 FTSA)

*Analysed as linear and branched isomers, and the sum of these.

Other variables:

- Plasma albumin concentration (as a mediator)

Independent Variables

- Study group identity (HFPDs, RFPDs, control group)

Statistical Analysis

Stata (StataCorp, College Station, TX, USA) will be used for the statistical analyses.

Outcome variables will be checked for normality. Normally distributed data will be expressed as mean (SD), and non-normally distributed data will be expressed as median (min-max and/or IQR). 95% confidence intervals will be used, and a two-tailed p-value < 0.05 will be considered statistically significant.

Samples below the detection and quantification limits:

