- The number, n (%), of samples below the limit of quantification (LOQ), as defined per the laboratory protocol, will be calculated.
- The number, n (%), of samples below the limit of detection (LOD) will be calculated.
- Only PFAS (or summarized variables) with a detection rate >70% at baseline will be included in the statistical analysis [14, 15].

For values below the LOD, a common imputation approach will be used where concentrations are replaced by LOD/2 (i.e., one-half the detection limit). Sensitivity analyses may be conducted to evaluate the choice of imputation method for values below the LOD (e.g., LOD/2, LOD/ $\sqrt{2}$, or exclusion of values below the LOD) to assess the robustness of the imputation strategies.

Branched isomers of PFHxS, PFHpS, PFOS, PFNS, PFDS, and PFOSA will be calculated as:
Branched = sum – linear.

The difference in PFAS concentrations within each group from baseline at W1 to the end point at W18 between the study groups will be estimated using generalized linear models (or similar methods). For continuous outcomes, we will use an identity link function and assume a Gaussian distribution family.

We will also consider analyses using other distribution families based on the skewness of the data, as well as whether to categorize (e.g., dichotomize) the outcome variable.

We will also consider quantile regression and express the effects as the median differences between the study groups.

Bootstrap confidence intervals (95%) for median concentrations and median changes will be calculated using 1,000 resampling iterations to provide robust estimates that are not sensitive to non-normality.

We will also use mediation analyses to estimate the extent to which the effect is mediated through changes in albumin concentration.

Results

Figures

Flow chart of participants and samples, including ITT and PP populations and the number of donations.

Plots showing the concentration of different PFAS from week 1 to week 18.

Tables

Table 1: Baseline characteristics

	HFPDs	RFPDs	Control group
Age			
Height			
Weight			
BMI			
Donation history			
• Plasma			
• Whole blood			
Occupation			

Table 2: Baseline concentration of PFAS (incl. branched and linear isomers)

	HFPDs	RFPDs	Control group
PFBA (ng/mL)			
...			

Table 3: Concentrations of PFAS at W18 and change from W1

PFAS	HFPDs		RFPDs		Control group	
	W18	W18-W1	W18	W18-W1	W18	W18-W1
PFBA (ng/mL)						
...						

*p-value compared to controls at W18

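### Read literally, Table 3's footnote ties the only p-value in a table shell to the W18 level, while the SAP defines and models the W1-to-W18 change

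*SAP*

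**What the plan says.** - **Outcome Measures.** The heading that covers all primary and secondary outcomes is "Difference in plasma concentrations between W1 and W18 of the following PFAS". There are five primary outcomes: four individual PFAS and their sum.
- **Independent Variables.** Study group is the only entry. The W1 concentration is not listed.
- **Statistical Analysis.** The modelled quantity is "The difference in PFAS concentrations within each group from baseline at W1 to the end point at W18 between the study groups". The method is generalized linear models or similar methods, with an identity link and Gaussian family for continuous outcomes. Concentrations as such appear only in the descriptive line "Bootstrap confidence intervals (95%) for median concentrations and median changes will be calculated using 1,000 resampling iterations".
- **Results, Tables.** The title is "Table 3: Concentrations of PFAS at W18 and change from W1". Each group has a W18 column and a W18-W1 column. The footnote is "p-value compared to controls at W18". In the text as extracted, no asterisk is visible in the table body and there is no p-value column.
- **Objectives.** The aim is to compare PFAS concentrations at baseline and after 16 weeks between the three groups. This can be read as a comparison of levels or of changes.

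**The concern.** Table 3 is where the outcome will be reported, and its own column heads use W18 for the level and W18-W1 for the change. A footnote that says W18 therefore points to the level. The SAP's outcome and model are the change.

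These are different tests. Both are unbiased under randomisation, but an unadjusted test of the W18 level ignores the donor's own W1 sample, so the two can give different verdicts on the same data. If the shell were completed exactly as worded, the p-values shown for the primary outcomes would not come from the analysis that the SAP specifies. A reader of the paper could not tell from the plan which contrast had been intended.

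**Working it through.** **1. Text check.** Tables 1, 2, S1 and S2 name no p-value, so the Table 3 footnote is the only one in a shell. The Statistical Analysis section specifies no between-group test of the W18 level. Set side by side:

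| Place in SAP | Quantity |
|---|---|
| Outcome Measures | W1-to-W18 difference |
| Statistical Analysis, model | W1-to-W18 difference, between groups |
| Table 3, columns | W18 and W18-W1, kept apart |
| Table 3, footnote | p-value against controls at W18 |

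**2. Are the two tests interchangeable as planned?** The SAP states no power or sample-size figure to reproduce, so what follows is an illustration.

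Inputs from the SAP:
- Two-sided significance level 0.05.
- "120 male blood donors were randomized 1:1:1", so 120 / 3 = 40 per arm at most.
- "Samples were analysed in two batches of 96 samples in 2023 and 122 samples in 2024", so 96 + 122 = 218 samples. If all are paired and the arms are equal, 218 / 2 / 3 = 36.3, taken as 36 per arm.

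Assumptions, because the SAP is silent: normal data, the same between-donor SD (set to 1) at W1 and W18, a group effect of 0.3 SD, and a range of W1-W18 correlations ρ.

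Variance of each analysis relative to the W18 level:
- W18 level, unadjusted: 1
- Change, unadjusted: 2(1 − ρ)
- Adjusted for W1: 1 − ρ²

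Power is from the two-sample noncentral t distribution with noncentrality 0.3 × √(36/2) / √(variance factor). For the level this is 0.3 × 4.243 / 1 = 1.27. For change at ρ = 0.9 it is 1.27 / √0.2 = 2.85.

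| ρ | Change, variance factor | W1-adjusted, variance factor | Power, W18 level | Power, change | Power, W1-adjusted |
|---|---|---|---|---|---|
| 0.3 | 1.4 | 0.91 | 24% | 19% | 26% |
| 0.5 | 1.0 | 0.75 | 24% | 24% | 31% |
| 0.8 | 0.4 | 0.36 | 24% | 51% | 55% |
| 0.9 | 0.2 | 0.19 | 24% | 80% | 82% |
| 0.95 | 0.1 | 0.0975 | 24% | 98% | 98% |

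At 40 per arm the level has 26%, and change has 26%, 55%, 84% and 99% at ρ = 0.5, 0.8, 0.9 and 0.95. The unadjusted level and change tests have equal power only at ρ = 0.5. Below that, change is the weaker test.

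**3. How often would the verdict differ?** In simulated two-arm trials with 36 per arm and the same assumptions, the level and change tests disagree on significance in about 26%, 43%, 62% and 75% of trials at ρ = 0.5, 0.8, 0.9 and 0.95. With no true effect they disagree in 8% to 9%. Even at ρ = 0.5, where power is equal, they disagree in about a quarter of trials: about 13% significant on change only and about 13% on level only.

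**4. What W1 adjustment does.** Write the change model as W18 − W1 = a + group + b·W1 + error. Moving W1 to the right gives W18 = a + group + (b + 1)·W1 + error. The group coefficient, its standard error and its p-value are identical. With W1 in the identity-link Gaussian model, the choice between level and change no longer affects the test.

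**The case against.** The strongest reply is that the governing text is clear. Outcome Measures and Statistical Analysis both specify change, and nothing suggests that a footnote in an empty shell overrides them. The asterisk may have sat on a W18-W1 column and been lost in extraction. With only two sampling times, a change can only be observed at W18, so the phrase may simply separate this comparison from baseline. The allowance for similar methods could also cover a repeated-measures model with a W18 contrast. All of this stands as a reason for caution, and it limits the point to an unclear shell. It does not remove it: the footnote's words are intact wherever the marker sat, the table itself separates level from change, and the SAP specifies no repeated-measures model.

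The Objectives can also be read as comparing levels, so a W18 comparison may be intended as an additional result. That stands too. It would go too far to require the W18 columns to be purely descriptive.

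The power figures are not evidence from this trial. At ρ = 0.5 the level test loses nothing to unadjusted change, and at ρ = 0.3 it is the stronger of the two.

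A reader might infer a high correlation from the half-lives of 1 to 5 years in Background and Rationale. Over 17 weeks, without new intake or donation, they imply 0.5^(17/52.18) = 80% to 0.5^(17/(5 × 52.18)) = 96% of the burden remaining. That describes the average level, not how closely donors keep their relative positions. A uniform proportional decline gives a correlation of 1 at either figure. What matters is how donors differ in intake and elimination, and assay error, and the SAP gives none of these.

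**Conclusion.** The mismatch holds: the shell's only p-value is worded for the W18 level, and the SAP's outcome and model are the W1-to-W18 change. Severity is minor, because the governing sections are clear and the footnote may be loose wording.

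A reader might infer that the trial will run the wrong test, or that a W18-level test would be biased. The document supports neither. The footnote names no test, the change analysis remains specified, and a level comparison is unbiased under randomisation.

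The cost of following the footnote literally depends on a correlation that the SAP does not give. Under the assumptions above it ranges from a gain of about 5 points of power against unadjusted change at ρ = 0.3, through none at 0.5, to a loss of about 74 points at 0.95. Against a W1-adjusted model, the unadjusted level test has less power at every correlation examined, from about 2 points at 0.3 to about 74 at 0.95.

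**What to change.** 1. Replace the Table 3 footnote with: *p-value for the between-group difference in W18-W1 change versus controls, from the generalized linear model*. Put its marker on the W18-W1 columns. If a comparison of W18 levels is kept to serve the objective, label it as additional.
2. Add the W1 concentration as a covariate in that model and list it under Independent Variables. Over unadjusted change the illustration gives gains of about 7, 6, 4, 2 and 0 points of power at correlations 0.3, 0.5, 0.8, 0.9 and 0.95, with no material loss at any of them. In the identity-link model, the group p-value is then the same whether the outcome is written as W18 or W18-W1.

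The first change alone cures the mismatch. The cost is one footnote and one sentence. No new data are needed, since the W1 samples are already collected.

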Statistical Analysis Plan (SOP)

Parent study Title: “The Effect of Plasma Donation Frequency on Plasma Protein Composition, Inflammation Markers and Psychological Distress - a Randomized Controlled Trial”

Sub Study Title: “The Effect of Plasma Donation Frequency on PFAS Concentrations – a randomized controlled trial”

ClinicalTrials.gov Reference: NCT05179200

Date: 01.09.2025

Introduction

Background and Rationale

Poly- and perfluoroalkyl substances (PFAS) are synthetic compounds used for their water- and fat-repellent properties in products such as textiles, food packaging, cosmetics, and electronics [1-3]. PFAS are highly persistent in the environment and the human body, with long biological half-lives of 1-5 years [4]. As a result, they are widely detected in drinking water, soil, and food. Exposure in humans primarily occurs through the ingestion of contaminated water and food, as well as through everyday consumer products such as non-stick cookware, water-repellent clothing, food packaging, dental floss, and cosmetics. PFAS are absorbed into the bloodstream and bind to proteins rather than fat [3, 5-7], leading to bioaccumulation over time [1, 8]. This accumulation has been linked to adverse health effects, including immune suppression, hormonal disruption, elevated cholesterol, and potential carcinogenicity [9].

PFAS exposure is primarily assessed through blood concentrations. A recent Swedish study investigated PFAS exposure in the general population and analysed samples from 60 blood donors [10]. They detected 26 of 30 different PFAS and observed PFHxS-lin, PFOS (linear and branched), PFOA-lin, PFNA, and PFDA in all samples, and found the highest concentrations of PFOS-lin, PFOS-br, PFOA-lin, and PFHxS-lin.

A previous RCT in Australian firefighters, with high exposure to PFAS through firefighting foams, demonstrated reductions in PFAS concentrations following plasma donations every 6 weeks and blood donations every 12 weeks [11].

In this study, we aim to investigate the effect of different plasma donation frequencies on PFAS concentrations in blood donors.

Objectives

To compare the plasma concentration of different PFAS at baseline and after 16 weeks of donations between high-frequency plasma donors (HFPDs), donating plasma 3 times every 2 weeks, regular-frequency plasma donors (RFPDs), donating plasma once every 2 weeks, and a control group (controls) donating whole blood every 3 months.

Study Methods

Trial Design

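### The aim is the effect of plasma donation frequency, but the SAP names no high- versus regular-frequency contrast, and Table 3 provides p-values against whole-blood controls only

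*SAP*

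**What the plan says.** The aim, at the end of Background and Rationale, reads: "we aim to investigate the effect of different plasma donation frequencies on PFAS concentrations in blood donors". The sub-study title has the same focus. The Objectives section is broader and lists all three arms; it begins "To compare the plasma concentration of different PFAS at baseline and after 16 weeks of donations between high-frequency plasma donors (HFPDs" and goes on to the regular-frequency donors and the controls.

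Trial Design defines two arms that give plasma, one with 24 planned donations and one with 8. The third arm differs in kind: "The control group (controls) donating whole blood every 3 months (in total 2 times").

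The Intervention section describes one plasmapheresis machine and one plasma volume, with no difference between the two plasma arms. Controls give 450 mL of whole blood.

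Under Independent Variables the only factor is the three-level "Study group identity (HFPDs, RFPDs, control group"). The Statistical Analysis section plans a generalized linear model for the W1 to W18 difference across the study groups, and may add quantile regression for median differences across the groups. Neither sentence gives a reference group or lists pairs.

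In the table shells the only between-group inference is the footnote to Table 3, "p-value compared to controls at W18". Table 3 has W18 and W18-W1 columns for each arm, and no between-group difference or confidence interval for any pair.

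**The concern.** The one comparison the SAP commits to reporting is narrower than its aim. A plasma arm and the control arm differ in two respects, donation type and donation schedule, so a small p-value against controls cannot be put down to plasma donation frequency. HFPD versus RFPD is the contrast that varies plasma frequency with the procedure held constant.

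If Table 3 is filled in as drawn, the paper will show two p-values per PFAS, both against controls, and no direct test between the plasma arms. A reader would then be left to compare the two p-values (one significant, one not, or both significant), and neither pattern tests whether donating more often changes PFAS further.

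**Working it through.** The SAP gives no sample-size or power figure on this point, so there is none to reproduce. The checks below ask whether the arms are described consistently, whether the planned model can give the contrast, and how far two control-referenced p-values can mislead.

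**1. What differs between the arms** (Trial Design; Intervention: about 650 mL plasma per plasmapheresis, 450 mL per whole-blood donation, haematocrit 44%)

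Donation counts over 16 weeks: 16/2 × 3 = 24 and 16/2 = 8, as stated.

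| Arm | Procedure | Donations | Planned plasma removed |
|---|---|---|---|
| HFPD | plasmapheresis | 24 | 24 × 0.65 = 15.6 L |
| RFPD | plasmapheresis | 8 | 8 × 0.65 = 5.2 L |
| Control | whole blood | 2 | 2 × 0.45 × (1 − 0.44) = 0.50 L |

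HFPD versus RFPD is a threefold difference in frequency with the same procedure. Because the period is fixed, cumulative volume also differs threefold, so the contrast measures frequency and volume together.

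**2. Is the contrast available from the planned model?**

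With a three-level factor and controls as reference, the coefficients are b1 = HFPD − control and b2 = RFPD − control. Then b1 − b2 = HFPD − RFPD, a linear combination of quantities already estimated. With n per arm and common standard deviation σ, every pairwise difference has the same standard error, σ√(2/n). "120 male blood donors were randomized 1:1:1 for donation over 16 weeks" gives n = 120/3 = 40, so the standard error is σ√(2/40) = 0.224σ for each pair. The direct contrast is as precise as either comparison with controls.

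**3. What size of difference could it detect?**

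The two-sided 5% level is from the SAP; 80% power is an assumption. The detectable difference is (1.960 + 0.842) × √(2/n), in SD units of the change.

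- n = 40: 2.802 × 0.2236 = 0.63 SD.
- n ≈ 36: the SAP reports 96 + 122 = 218 samples; if all are paired (an assumption), that is 109 men, about 36.3 per arm, giving 0.66 SD.
- With a Bonferroni correction over three contrasts (2.394 in place of 1.960): 0.72 SD and 0.76 SD.

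**4. Why two p-values against controls do not answer the question**

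When the standard errors are equal, the z-value of the direct contrast is the difference of the two control-referenced z-values. The values below are illustrations, not predictions.

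| HFPD − control | RFPD − control | HFPD − RFPD |
|---|---|---|
| 3.0 SE, p = 0.003 | 1.5 SE, p = 0.13 | 1.5 SE, p = 0.13 |
| 5.0 SE, p < 0.001 | 2.5 SE, p = 0.012 | 2.5 SE, p = 0.012 |

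In the first row Table 3 would suggest that only the higher frequency works, while the direct evidence for a difference between frequencies is weak. In the second row both arms are significant and Table 3 would appear to show no distinction, although the direct contrast is itself significant and would not be shown.

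**The case against.** A reader might infer from Table 3 that HFPD versus RFPD will receive no estimate or test at all. The SAP does not support that. Its objective covers three groups, its factor has three levels, and its model text speaks of the study groups in general, with nothing restricting the comparison to controls. A footnote in an empty table shell does not override the methods text. The shell is plainly not exhaustive: it shows no between-group estimate or interval even for the control comparisons.

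It can also be said that comparing with controls is a proper part of the three-group objective; that frequency and volume are not separated even within the plasma arms; that nobody has said a frequency conclusion would be drawn from two p-values; and that Table 3 will show each arm's change, from which the HFPD-RFPD difference can be read by eye.

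Most of this stands. The contrast is covered in general terms, the control comparisons are legitimate, and the numerical scenarios are illustrative. What it does not remove is that the SAP becomes specific about a between-group comparison in one place only, and there it chooses controls. Changes by arm, even with bootstrap intervals for the medians, are not an interval or test for the difference between arms.

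**Conclusion.** The concern holds in a limited form. HFPD versus RFPD can be estimated from the planned model with the same precision as the control contrasts, but the SAP does not name it and its tables have no place for it, while the only reported p-value is against controls who also differ in donation type. The stated frequency question could therefore go without a reported direct test. This should be changed; it is not a defect of the design or of the model, and it would be wrong to say that the plan rules the contrast out.

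The precision statements assume equal analysed arms and equal variances. The SAP does not give the analysed arm sizes, and 218 samples is fewer than the 240 that 120 men sampled twice would provide. The scenarios in SE units rest on the same assumptions and use no effect or variance from the SAP. The contrast isolates plasma frequency only in the sense that the procedure is constant; cumulative volume changes with it.

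**What to change.** In Statistical Analysis, name the pairwise contrasts and include HFPD versus RFPD on the W18-W1 change, taken from the planned three-group model. In Table 3, add its estimate, 95% CI and p-value for each primary PFAS, next to the same quantities for the two control contrasts. State that conclusions about plasma donation frequency rest on this contrast and not on comparing the two p-values against controls.

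The cost is one linear combination per PFAS and one block of table columns; no new data or model is needed. The downside is one more contrast per outcome: counting the five listed primary outcomes once each, 3 × 5 = 15 primary p-values instead of 2 × 5 = 10. The SAP gives a 0.05 threshold and describes no multiplicity procedure, so the amendment should say how the contrasts are handled and not refer to an existing procedure. The SAP schedules the analysis for September 2025; if it has begun, the addition should be dated and reported as such.
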